2.6.4 Data and Safety Monitoring Committee

A data safety monitoring board (DSMB) will not be necessary for this research protocol. Research in this pilot study poses no more than minimal risk to participants. There will be no statistical monitoring to determine whether the clinical trial should be terminated for reasons of safety. There will be no interim evaluations for efficacy. There are no planned stopping rules for futility since this is a pilot study. Safety monitoring will focus on ensuring participants are not experiencing any significant or unexpected psychological distress and that they are satisfied with the study intervention and interviews. The Principal Investigator will provide ongoing observation for psychological distress as reported in satisfaction surveys or during interviews. The PI will monitor for Adverse Events related to the study, but there is a very low risk for adverse events with the proposed intervention. [name] has three years of experience as a medical monitor for the Cystic Fibrosis Foundation Therapeutics Development Network Coordinating Center, and is well-qualified to review and make a determination of relatedness of a serious adverse event (SAE) to the study intervention.

3.0 RISK ANALYSIS

3.1 Anticipated risks

Subjects may be exposed to minimal risks associated with the conduct of this study.

Psychological risks: Given the sensitive nature of LTx as a treatment option for CF, it is possible that patients may experience psychological distress from reading about transplant, especially in cases where CF patients have died after LTx. We have worked to mitigate this risk by allowing participants to moderate the amount of information they read about particular patient stories or ‘Resource Library’ content. Specifically, we have applied labels to ‘CF Stories’ with a “bad outcome” or “death,” which are visible prior to entering the story. Additionally, over the course of a participant’s involvement in this research study we will monitor mental health by administering mental health assessments, including the PHQ-9 survey. It is possible that a participant may experience psychological discomfort by completing these assessments. To protect a participant’s wellbeing, if abnormal results are reported in the PHQ-9 the UW research team will notify their CF doctor for follow-up care.

There is no proven benefit of ToT at this time, but a prior (now outdated) decision aid for LTx in CF showed a reduction in decisional conflict and we hypothesize that the proposed intervention will increase preparedness for decision making and decrease decisional conflict related to LTx. Further, this pilot study will provide important feedback to optimize ToT for future users.

3.2 Adverse event reporting

3.2.1 Adverse event definitions

An adverse event (AE) is any untoward medical occurrence in a clinical investigation of a patient administered a pharmaceutical product or undergoing an investigational procedure that does not necessarily have a causal relationship with the treatment or procedure. An AE is therefore any unfavorable and unintended sign (including an abnormal laboratory finding), symptom or disease temporally associated with the administration of an investigational product or procedure, whether or not related to that investigational product. An unexpected AE is one of a type not identified in nature, severity, or frequency in the currently accepted risk profile for the treatment or procedure.

An unanticipated problem (UP) is defined as any incident, experience, or outcome that meets all of the following criteria:

1. unexpected (in terms of nature, severity, or frequency) given (a) the research procedures that are described in the protocol-related documents, such as the IRB-approved research protocol and informed consent document; and (b) the characteristics of the subject population being studied;
2. related or possibly related to participation in the research (in this guidance document, possibly related means there is a reasonable possibility that the incident, experience, or outcome may have been caused by the procedures involved in the research); and
3. suggests that the research places subjects or others at a greater risk of harm (including physical, psychological, economic, or social harm) than was previously known or recognized.

An SAE is defined as any untoward medical occurrence that at any level of procedural intensity:

1. Results in death
2. Is considered life threatening (i.e., in the view of the Investigator the adverse experience places the patient or participant at immediate risk of death from the response, as it occurred; it does not include a reaction that, had it occurred in a more severe form, might have caused death)
3. Requires hospital admission or prolongation of an existing hospitalization
4. Results in persistent or significant disability/incapacity (i.e., a substantial disruption of a person's ability to conduct normal life functions)
5. Is an important medical event (i.e., when based upon appropriate medical judgment, the adverse experience may jeopardize the patient or participant and

may require medical or surgical intervention to prevent one of the above listed outcomes)

For the purposes of the proposed study, participant report of possible suicidality on the PHQ-9 is an immediately reportable AE, even if it is not an SAE. An alternative approach would be to utilize the PHQ-8 (which excludes the question about suicide), but it is important to understand whether there is a risk of increasing suicidality through the introduction of LTx education in this patient population. Avoiding the question in our study will not prevent the thoughts/feelings from occurring and we determined that it is in the interest of patient safety to include the question about suicidality and have a plan in place for responding in the case of this AE of special interest.

3.2.3 Recording and assessment of adverse effects

The Principal Investigator and/or research team staff will probe, via discussion with the participant, for the occurrence of AEs/UPs during each participant visit/call and record the information in the study's records. AEs will be described by duration (start and stop dates and times), severity, outcome, treatment and relation to study procedure, or if unrelated, the cause.

All observed or volunteered adverse events (serious or non-serious) and abnormal test findings, regardless of treatment group, if applicable, or suspected causal relationship to the investigational device or, if applicable, other study treatment or diagnostic product(s) will be recorded in the subjects' case histories. For all adverse effects, sufficient information will be pursued and/or obtained so as to permit 1) an adequate determination of the outcome of the event (i.e., whether the effect should be classified as a *serious adverse event*) and; 2) an assessment of the causal relationship between the adverse effect and the investigational device or, if applicable, the other study treatment or diagnostic product(s).

3.2.5 Causality and severity assessment

The National Cancer Institute's Common Terminology Criteria for Adverse Events (CTCAE) Version 4.03, as modified for CF, will be used to assess and grade AE severity, including laboratory abnormalities judged to be clinically significant. If the experience is not covered in the modified criteria, the guidelines shown in Table 1 below will be used to grade severity. It should be pointed out that the term "severe" is a measure of intensity and that a severe AE is not necessarily serious.

Table 1. Adverse Event Severity Grading

Severity (Toxicity Grade)	Description
Mild (1)	Transient or mild discomfort; no limitation in activity; no medical intervention or therapy required. The participant may be aware of the sign or symptom but tolerates it reasonably well. (e.g. fatigue during study visit)
Moderate (2)	Mild to moderate limitation in activity, no or minimal medical intervention/therapy required. (e.g. psychological discomfort during study visit that may lead to crying or other emotional displays)
Severe (3)	Marked limitation in activity, medical intervention/therapy required, hospitalizations possible. (e.g. profound symptoms of anxiety or depression prompting hospitalization)
Life-threatening (4)	The participant is at risk of death due to the adverse experience as it occurred. This does not refer to an experience that hypothetically might have caused death if it were more severe. (e.g. suicidality that leads to a suicide attempt)

The relationship of an AE to the study procedure should be assessed using the following the guidelines in Table 2.

Table 2. Adverse Event Relationship to Study Procedure

Relationship to study procedure	Comment
Definitely	Previously known risk of procedure; or an event that follows a reasonable temporal sequence from performance of the procedure/testing; that follows a known or expected physiologic response to the procedure; that is confirmed by stopping or reducing the intensity of the procedure; and that is not explained by any other reasonable hypothesis.
Probably	An event that follows a reasonable temporal sequence from performance of the procedure; that follows a known or expected physiologic response to the procedure; that is confirmed by stopping or reducing the intensity of the procedure; and that is unlikely to be explained by the known characteristics of the participant's clinical state or by other interventions.
Possibly	An event that follows a reasonable temporal sequence from performance of the procedure; that follows a known or expected physiologic response to the procedure; but that could readily have been produced by a number of other factors.
Unrelated	An event that can be determined with certainty to have no relationship to the study procedure.

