2.5.8 Procedures to assess safety

We will assess safety using the PHQ-9[12] and GAD-7[9] survey assessments.

The topic of LTx can be distressing to some with CF. There could be a risk of increasing depression symptoms and/or suicidality through the introduction of LTx education in this patient population. The PHQ-9 and GAD-7 surveys will be administered at the baseline visit (V1) and at both study visits (V2, V3) after patients gain access to ToT or unos.org to assess whether introduction of transplant education has a negative psychological impact on patients including an increase in anxiety, depression, and/or distress. Patients with an abnormal PHQ-9 or GAD-7 will be allowed to enroll in the study because depression and anxiety are prevalent in advanced CF lung disease. We hypothesize use of ToT may actually lessen patients' depression and/or anxiety with time.

The interviewer (UW research staff) will review PHQ-9 responses immediately after responses are submitted. The interviewer will also probe, via discussion with the participant, for any indicators of negative psychological impacts of use of the decision support tool. If possible suicidality is endorsed on the PHQ-9 (positive response to question #9), the interviewer will provide a subject who endorses possible suicidality with the National Suicide Hotline phone number and will inform them to call the National Suicide Hotline if they need help prior to receiving the call from [name] or another study physician about the PHQ-9 results. Additionally, the PI, or another study physician, will be notified immediately after the abnormal PHQ-9 result is entered. The patient's CF clinician will be contacted directly immediately via secure communication, by the PI, in the setting of possible suicidality. The PI or another study physician will call the patient within 8 hours of a PHQ-9 response that indicates suicidality and the Columbia-Suicide Severity Rating Scale (C-SSRS) screen with triage points for primary care will be completed. The C-SSRS response protocol will be followed and a safety contract will be established with the patient by the physician by phone. [name], and the other study physicians, are trained physicians, practicing medicine in populations with advanced diseases, end of life concerns, and high rates of mental illness. [name] has clinical experience with patients who report suicidality and has the resource of a trained CF mental health specialist for complex cases.

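### Table 2 offers no clear intermediate relatedness rating for psychological events, the harms this website trial anticipates, and its *Possibly* differs from section 3.2.1

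*Combined protocol and SAP*

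**What the plan says.** Section 3.2.5 makes Table 2 the guide to causality: "The relationship of an AE to the study procedure should be assessed using the following the guidelines in Table 2". The table has four categories.

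- *Definitely* opens with "Previously known risk of procedure; or an event that follows a reasonable temporal sequence from performance of the procedure/testing". It then asks for a physiologic response, confirmation on stopping, and no other reasonable explanation.
- *Probably* asks for suitable timing and an event "that follows a known or expected physiologic response to the procedure; that is confirmed by stopping or reducing the intensity of the procedure", with other causes unlikely.
- *Possibly* asks for suitable timing and an event "that follows a known or expected physiologic response to the procedure; but that could readily have been produced by a number of other factors".
- *Unrelated* is "An event that can be determined with certainty to have no relationship to the study procedure". No category lies between this and *Possibly*.

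The harms the protocol anticipates are psychological. Section 3.1 says "it is possible that patients may experience psychological distress from reading about transplant". Section 2.5.8 says "There could be a risk of increasing depression symptoms and/or suicidality through the introduction of LTx education in this patient population". Three of the four examples in Table 1 are psychological: crying during a visit, anxiety or depression leading to hospitalization, and a suicide attempt.

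Section 3.2.1 gives a different meaning when it defines an unanticipated problem: "possibly related means there is a reasonable possibility that the incident, experience, or outcome may have been caused by the procedures". It sets no physiologic condition and counts psychological harm.

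Section 3.2.3 requires each adverse event to be described by its relation to the study procedure. Section 2.6.4 provides no DSMB and leaves the relatedness of serious events to an experienced medical monitor.

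**The concern.** Table 1 has been adapted to this trial, with examples such as crying at a visit. Table 2 has not. Its two middle categories depend on a physiologic response, which is not the natural description of distress after reading about transplant. The middle categories are where most honest judgements would fall in people with advanced lung disease, among whom section 2.5.8 says depression and anxiety are prevalent. A rater following the table as written is pushed towards *Definitely* or finds no category that fits. Two careful raters could then grade the same event differently. At stake is whether the recorded relatedness of psychological events reflects the events or the wording of the scale.

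**Working it through.** No arithmetic in the plan bears on this point, so the check is logical. Table 2 was coded as conditions and every combination listed.

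**Inputs (all from Table 2).** Known risk (yes/no); suitable timing (yes/no); physiologic response (yes/no); confirmed on stopping (yes/no); other explanation (none, unlikely, readily available). The event is taken as not certainly unrelated, so *Unrelated* is closed.

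**Two readings of *Definitely*.** The opening alternative can be read in two ways.

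- Reading A: known risk is enough by itself, or all the other criteria are met.
- Reading B: known risk or timing, and in either case all the remaining criteria.

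**Count.** With known-risk status and the physiologic condition fixed, there are 2 (timing) × 2 (confirmed on stopping) × 3 (other explanation) = 12 combinations.

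| Physiologic condition not met | Reading A | Reading B |
|---|---|---|
| Known risk | *Definitely* in 12 of 12 | No category in 12 of 12 |
| Not a known risk | No category in 12 of 12 | No category in 12 of 12 |

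*Probably* and *Possibly* are never reached under either reading. Under reading A, the 12 for a known risk include events with no suitable timing and events that other factors could readily explain.

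**Sensitivity: a psychological reaction is accepted as physiologic.** *Probably* and *Possibly* then become reachable. Under reading A:

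- A known risk still qualifies as *Definitely* in 12 of 12. It also meets *Probably* in 2 of these and *Possibly* in another 2, so the categories overlap.
- An event that is not a known risk still has no category in 8 of 12. Six of these lack suitable timing. The other 2 have it, and other causes are absent or unlikely, but there is no confirmation on stopping. Those 2 fail *Probably* for want of confirmation and fail *Possibly* because no other factor readily explains them.

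**The two meanings of possibly.** Section 3.2.1 asks only for a reasonable possibility of causation. Table 2 asks for a response that is known or expected. A harm unexpected in nature can satisfy the first and not the second, however broadly the word physiologic is read.

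**Where the grade is used.** Section 3.2.3 records it and section 2.6.4 relies on such a determination for serious events. Section 3.2.6 sends serious events within 48 hours of a visit, and all reported suicidality, to the IRB without a relatedness condition. Serious events at other times are captured but not reported. If visits fall on days 0, 14 and 28, the 48-hour windows cover at most about 2 + 4 + 2 = 8 of the 28 days. For serious events on other days, suicidality apart, the recorded grade may be the only causal judgement.

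**The case against.** The strongest reply is that Table 2 is guidance for a qualified physician and not an algorithm. Table 1, in the same section, uses psychological examples, so the section was evidently meant to cover them, and a sensible rater would read physiologic broadly. Safety is assessed mainly with PHQ-9 and GAD-7, compared between randomized arms (sections 2.5.8 and 2.6.1), and section 2.6.3 plans no tabulation of relatedness.

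Much of this stands and limits the point. It does not remove it. The documents nowhere say that physiologic includes psychological reactions, and the broad reading leaves the known-risk route and the gaps shown above.

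A reader might infer more than the documents support:

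- *That every related category needs a physiologic response.* On the reading that lets known risk stand alone, *Definitely* does not. On the reading where the condition applies throughout, nothing becomes *Definitely* by default. The two claims cannot be held together.
- *That suicidality is automatically rated Definitely.* Section 2.5.8 says only that there could be a risk, and section 3.2.1 treats it as a question to be understood. Whether it is a previously known risk is unclear.
- *That distress present before website access would be rated Definitely.* Section 3.2.1 defines an adverse event by its temporal association with the product or procedure, so such distress would ordinarily not be graded.
- *That the unanticipated-problem test fails.* It carries its own definition and does not refer to Table 2.

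**Conclusion.** The point holds as a mismatch between one table and the harms the trial anticipates. Read literally, a psychological event that is not certainly unrelated cannot be rated *Probably* or *Possibly*. If known risk alone suffices, an anticipated event such as distress can be rated *Definitely* regardless of timing or other causes. An event that is not a known risk has no clear category. Separately, *Possibly* in Table 2 and possibly related in section 3.2.1 differ and should be reconciled.

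The conclusion rests on two assumptions: that physiologic does not include psychological reactions, and, for the *Definitely* result, that known risk stands alone. Relaxing the first narrows the problem without removing it. Relaxing the second leaves such events ungraded.

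The size is modest. The effect is on the relatedness recorded under section 3.2.3 and the determination for serious events in section 2.6.4. The endpoints, the PHQ-9 and GAD-7 comparisons, suicidality reporting, reporting of serious events within 48 hours of a visit and the unanticipated-problem definition do not use the grade. The change is worth making because it is cheap and the rule as stated cannot be followed consistently.

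**What to change.** Amend Table 2 as follows.

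1. Replace the physiologic condition wherever it appears with wording that covers a known, expected or plausible psychological or physical response to the website, interviews or surveys.
2. Remove the stand-alone known-risk alternative, so that *Definitely* always needs suitable timing and no other reasonable explanation.
3. Define *Possibly* by the section 3.2.1 standard of a reasonable possibility of causation.
4. Apply the confirmation-on-stopping condition only where it can be assessed. Without this, step 2 would cap one-time events, such as a suicide attempt, at *Possibly*.

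Redefining *Unrelated* as no reasonable possibility is optional and partly a choice of scale. It would complement step 3, so that every event has a category.

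The cost is a wording amendment to one table, with no new data, visits or staff. The downside is that adverse events already graded would need re-grading.

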3.2.6 Reporting adverse effects to the responsible IRB

All unanticipated problems that are SAEs (whether procedure related or not) that occur within 48 hours of a study visit will be documented and reviewed by the Investigator within 24 hours. SAEs that occur not within 48 hours of a study visit will be captured through patient's self-report at the next study visit, but will not be reported. All SAEs within 48 hours of a study visit will be sent the UW IRB within 24 hours. Reporting of unanticipated problems that are SAEs to the IRB will be performed by the Investigator in accordance with the standard operating procedures and policies. Adequate documentation will be provided showing that the IRB was properly notified. All episodes of reported suicidality documented on PHQ-9 administered during study visits, or patient report of suicidality between study visits, will be reported to the UW IRB within 24 hours.

Additionally, the patient's CF clinician will be contacted directly immediately via secure communication, by the PI ([name]), and a study physician will establish a safety contract with the patient by phone in the interim within 8 hours of becoming aware of an abnormal result.

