Research website – Participants will be introduced to the research website during the baseline session (V1). The research website is a portal that will contain links to two interventions including ToT and an attention control (unos.org). Before accessing the research website during the baseline session, participants will be randomized to first receive access to only one of the two websites through the portal. The research website will track website usage (i.e. time spent, content accessed, etc.) for all study participants for both ToT and unos.org. Once the participant completes the 2-week study visit (V2), the portal will contain access to both ToT and unos.org for the remainder of the study (2 more weeks).

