8.0 IRB INFORMATION

This pilot RCT was reviewed and approved by the University of Washington Human Subject's Division IRB. Collaborating institution who distributed screening surveys for recruitment purposes were considered not engaged per HHS guidelines and did not require additional IRB approval from their local IRBs.

Any documents that the IRB may need to fulfill its responsibilities (such as protocol, protocol amendments, consent forms, information concerning patient recruitment, payment or compensation procedures, or other pertinent information) will be submitted to the IRB. The IRB's written unconditional approval of the study protocol and the informed consent form will be in the possession of the Investigator before the study is initiated.

Protocol and/or informed consent modifications or changes may not be initiated without prior written IRB approval except when necessary to eliminate immediate hazards to the patients or when the change(s) involves only logistical or administrative aspects of the study. Such modifications will be submitted to the IRB and written verification that the modification was submitted and subsequently approved should be obtained.

The IRB must be informed of revisions to other documents originally submitted for review; new information that may affect adversely the safety of the patients of the conduct of the study; an annual update and/or request for re-approval; and when the study has been completed.

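### Suicidality apart, section 3.2.6 gives opposite answers on whether a related, unexpected SAE more than 48 hours from a visit goes to the IRB

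*Combined protocol and SAP*

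**What the plan says.** Section 3.2.6 contains four rules that bear on this point:

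- **Outside the window.** The rule for SAEs reads: "not within 48 hours of a study visit will be captured through patient's self-report at the next study visit, but will not be reported".
- **Inside the window.** Every SAE goes to the IRB within 24 hours, with no condition on relatedness.
- **Unanticipated problems.** Reporting of "unanticipated problems that are SAEs to the IRB will be performed by the Investigator in accordance with the standard operating procedures and policies". No time window is attached. A separate sentence, on review by the investigator, is limited to the 48-hour window and begins "All unanticipated problems that are SAEs (whether procedure related or not" (the bracket closes there).
- **Suicidality.** Suicidality on a PHQ-9 at a visit, or "patient report of suicidality between study visits, will be reported to the UW IRB within 24 hours". Section 3.2.1 also makes possible suicidality on the PHQ-9 immediately reportable, even when it is not an SAE.

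Section 3.2.1 defines an unanticipated problem by three criteria that must all hold. It is unexpected in nature, severity or frequency; it is "related or possibly related to participation in the research"; and it suggests a greater risk than was known. Timing is not among them.

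Section 8.0 requires the IRB to be told of "new information that may affect adversely the safety of the patients of the conduct of the study". Section 3.2.3 has all adverse events recorded, serious or not, with an assessment of causality.

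**The concern.** The out-of-window rule filters on timing alone. Section 3.1 names distress from reading about transplant as a hazard, and reading is not confined to visits. Participants can use their assigned website for the first two weeks (section 2.5.3), and after the second visit "the portal will contain access to both ToT and unos.org for the remainder of the study" (section 2.5.2). A harmful reaction could therefore arise on any day.

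At stake is whether the IRB learns of a serious, related and unexpected event. Section 2.6.4 provides for no DSMB and leaves monitoring to the principal investigator, so the IRB is the main route in the protocol to safety review outside the study team. Staff following section 3.2.6 cannot tell from its text whether to send such an event.

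**Working it through.** The plan gives no figure to reproduce here; the check is a comparison of texts.

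**Test case.** Assume visits on days 0, 14 and 28, from the three sessions over four weeks in section 2.5.2. Take an SAE on day 7. It is 7 days, or 7 × 24 = 168 hours, from the nearest visit on either side. It is outside 48 hours whether the window runs only after a visit or on both sides of it.

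**Rules applied to each kind of event:**

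| Event | Out-of-window rule (3.2.6) | Unanticipated-problem sentence (3.2.6) | Other provision |
|---|---|---|---|
| Day 7 SAE meeting all three criteria of 3.2.1 | Not reported | Reported, no deadline stated | 8.0: general duty, no deadline |
| Day 7 SAE, related but not meeting all three criteria | Not reported | Does not apply | 8.0: general duty, no deadline |
| Day 7 SAE, unrelated | Not reported | Does not apply under 3.2.1 | 8.0 unlikely to apply |
| Suicidality reported on day 7 | Overtaken by the specific rule | Not needed | 3.2.6: IRB within 24 hours |
| Any SAE within 48 hours of a visit | Does not apply | Not needed | 3.2.6: IRB within 24 hours |

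**Reading the table.**

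1. The first row is the contradiction: two sentences of one section give opposite instructions for the same event.
2. Nothing in the text ranks them. The unanticipated-problem sentence refers to operating procedures that are not in the documents.
3. Section 8.0 does not break the tie. It has no time window, but it does not say that a single SAE is enough to trigger it.
4. Relatedness is already assessed (sections 2.6.4, 3.2.3 and 3.2.5), but the out-of-window rule makes no use of it.

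**A second mismatch.** The investigator-review sentence describes unanticipated problems as related or not, while section 3.2.1 makes at least possible relatedness part of the definition. Either the phrase is wrong, or the sentence was meant to cover all SAEs. Because it governs review and not IRB reporting, this is a minor wording error.

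**The case against.** The strongest reply is that an ordinary reading removes the conflict: the unanticipated-problem sentence governs unanticipated problems, the 48-hour rule governs all other SAEs, and the operating procedures may say so. That reading is sensible and may be what was intended. It stands as a reason to call this an ambiguity and not a proven failure to report. It does not remove the need for a change, because the out-of-window rule is worded for SAEs in general and the priority is not stated.

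A window tied to visits in a study described as minimal risk is also a legitimate design choice. Section 3.1 mentions discomfort from completing the assessments, which gives such a window some logic. The point here is only that it should not override the rule on unanticipated problems.

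A reader might infer more than the documents support, in three ways:

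- *That only section 8.0 remains outside the window.* This is not so. The suicidality rules apply at any time, and the unanticipated-problem sentence is still in the text.
- *That a related admission for anxiety or depression would slip through as an anticipated event.* Section 3.1 anticipates distress and discomfort, not admission, and section 3.2.1 counts unexpected severity. Such an event could well be an unanticipated problem. Its appearance in Table 1 illustrates a severity grade; it does not list an expected risk.
- *That the share of study days outside the window measures the problem.* It counts calendar days, not events.

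**Conclusion.** The point holds as an internal contradiction about IRB notification and should be corrected. It applies to SAEs that meet the section 3.2.1 definition, occur more than 48 hours from a visit, and are not covered by the suicidality rules. For these the protocol says both that the IRB is told and that it is not, and it sets no deadline for telling it.

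The consequences are limited. The events are still recorded, and no endpoint, estimate or analysis changes. The number affected cannot be given without an SAE rate and may be small or zero in about 50 participants followed for four weeks. The conclusion rests on the protocol text alone; operating procedures outside the documents may already settle the priority, in which case the protocol need only say so.

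**What to change.** Reconcile sections 3.2.1, 3.2.6 and 8.0 as follows:

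- State that an SAE meeting the section 3.2.1 definition of an unanticipated problem is reported to the IRB whenever it occurs during study participation. Use the 24-hour limit already in section 3.2.6, running from the time staff become aware of the event.
- Limit the no-report rule to the remaining SAEs outside the window, and say that the section 8.0 duty still applies to them.
- Keep the present reporting of SAEs inside the window and of suicidality.
- Reconcile the bracketed phrase on relatedness in the investigator-review sentence with section 3.2.1. Correct either the phrase or the term for the events it covers; the documents do not show which was meant.

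The sponsor may also consider whether related SAEs that are not unanticipated problems should be reported outside the window. The documents do not require this, and it would cost more. Table 2 in section 3.2.5 reserves its unrelated category for "An event that can be determined with certainty to have no relationship to the study procedure", so some ordinary CF admissions might be classed as possibly related and have to be sent.

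The cost of the main change is a wording amendment and possibly a few more IRB reports, a number that cannot be estimated from the documents. It uses causality assessments already planned and events staff already ask about at visits and calls. It adds no visits and no follow-up after the last session.
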